#### **5.5. Contributors and collaborators**

Participants will be recruited by research assistants who the main researcher will train in the intervention. The main researcher ([name]) will analyse transcripts with thematic analysis (which will then be discussed with other research collaborators), undertake the statistical analysis (potentially with support from a statistician) and write the manuscript (potentially with the assistance of others). Associate [name] will assist with the analysis of the brain scans. [name] and [name] will help with recruitment as they work clinically in Region Uppland and Region Västmanland and together with [name], [name] and Associate [name] comment on the final article.

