#### **5. Project description**

##### **5.1. Participants, sample size, settings and ethics**

Eligible participants will be over the age of 18 with a diagnosis of schizophrenia, delusional disorder or non-affective psychosis in Region Sörmland, Region Västmanland and Region Uppland. Exclusion criteria will be evidence of severe organic brain dysfunction or a learning disability, difficulty with the Swedish language, visual and/or hearing impairment, or being unable or unwilling to provide written informed consent. Clinical teams will be approached by [name] or a research assistant and asked to inform suitable patients about the study. The research assistant will then meet the subjects and inform them (both orally and written) prior to gaining written consent. Subjects who have been allocated to the control group (i.e. supportive counselling) will be offered metacognitive training after the trial has finished if they request this. We have used t/z-test, with a power of 0,85, and a significance level of 0,05, to calculate sample size. In order to find a difference of 4 units on CAINS (as a change in total score of 4 points has been found to show a true change at a 95% confidence level in previous research (Laraki et al., 2022)), 41 participants in each arm will be needed. We will aim to recruit 45 in each arm to allow for drop-out, group heterogeneity and to make future analysis (e.g. on the effect of medication) possible. Ethical approval will be applied for at the Etikprövningsmyndigheten.

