#### **5.4. Procedure**

Written informed consent, relevant demographic information and baseline measures will be completed before beginning the intervention. The Motivation and Pleasure Scale—Self-Report (MAP-SR) (Llerena et al., 2013) will be used to certify that some level of negative symptoms exist prior to the intervention. The patients will be randomised to either MCT Minus and treatment as usual or supportive counselling combined with treatment as usual using an online calculator. Pre-, post-, and follow-up assessments will be conducted by a research assistant who is blind to group allocation. Exit interviews will be held after completing the intervention where a standardized interview schedule (with open-ended questions) will be applied to minimize variations in questions asked while retaining enough flexibility to assess individual experiences (Patton, 1987). The head of the division psychiatry in the regional health board (Region Sörmland) has approved the study and there are structures (e.g. funding, research time, support from clinicians and managers) that would facilitate recruitment and feasibility.

During the pre and post assessment visits, the patients will also undergo a magnetic resonance imaging (MRI) investigation, including anatomical (T1-weighted) imaging, resting-state functional MRI to assess changes in default mode network connectivity after the active compared to control intervention, and additionally diffusion weighted imaging (DWI) and MR spectroscopy (MRS) to relate the functional connectivity findings to structural connectivity and prefrontal glutamate levels.

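### Does using research assistants both as trained recruiters and as the blind assessor undermine the blinding of the CAINS and PANSS ratings?

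*Protocol*

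**What the plan says.** Section 5.4 of the protocol fixes who rates the outcomes: "Pre-, post-, and follow-up assessments will be conducted by a research assistant who is blind to group allocation". Section 5.5 describes the recruiting staff: "Participants will be recruited by research assistants who the main researcher will train in the intervention". Section 5.1 describes the contact before consent: "The research assistant will then meet the subjects and inform them (both orally and written) prior to gaining written consent".

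On the qualitative part, section 5.4 says "Exit interviews will be held after completing the intervention where a standardized interview schedule (with open-ended questions) will be applied". It names no interviewer and does not place the interview before or after the post or follow-up ratings. Section 5.5 has the main researcher analyse the transcripts and "undertake the statistical analysis (potentially with support from a statistician").

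Section 5.3 names three primary measures: CAINS, the PANSS negative factor and MAP-SR. The first two are rated by an assessor and the third is self-report. Section 1 lists a blinded assessor among the features that set this trial apart from the feasibility study.

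**The concern.** Read quickly, sections 5.1, 5.4 and 5.5 give one job title three tasks: recruiting patients, being trained in MCT Minus, and rating outcomes blind. The protocol never says who delivers either therapy. The only staff described as trained in the intervention are the research assistants, so a reader may infer that they are the therapists and that a therapist could also be the rater. The exit interviews cover the patient's experience of the therapy, so whoever holds them could learn the arm. If that person later rates the same patient, the follow-up rating would no longer be blind.

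This would matter. Section 5.1 offers controls the training afterwards on request, so participants can be expected to know their arm and MAP-SR has no protection from blinding. Assessor blinding is the only blinding the protocol describes, and CAINS, on which the sample size rests, depends on it. A rater who expects MCT Minus to work could produce a difference between the arms without any treatment effect.

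**Working it through.** The question is mainly one of reading, so the statements are set side by side first.

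| Element of the concern | What the protocol states | Does it follow? |
|---|---|---|
| The assessor is one of the trained recruiters | 5.4: one assistant, blind. 5.5: assistants in the plural, trained, who recruit | No. The job title is shared, but no text says the person is |
| The trained assistants deliver the therapy | No section names the therapists | Plausible inference, not stated |
| Recruiting compromises blinding | 5.1: patients are informed before consent. 5.4: consent and baseline measures precede the intervention | No. Contact before randomisation carries no knowledge of the arm |
| Exit interviews come before follow-up | 5.4: only that they come after the intervention is completed | Not stated. An interview after the follow-up rating also fits |
| The assessor conducts or sees the interviews | 5.4: interviewer not named. 5.5 and 6.2: transcripts go to the main researcher | Not stated |
| The main researcher reads transcripts and runs the statistics | 5.5 | True, but this role is not described as a rater, so it does not bear on assessor blinding |

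Sections 5.4 and 5.5 can both be true at once: several assistants, with one kept blind to do the ratings. There is no contradiction to reconcile.

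**What would be at stake if blinding failed.** The protocol gives no SD for CAINS, but its other inputs imply one. With a difference of 4, power 0.85, two-sided 0.05 (the protocol does not state the sidedness) and 41 per arm:

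SD = 4 × √(41/2) / (1.960 + 1.036) = 6.04 by the normal formula, or 5.97 by the t-test.

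Take SD 6. The standard error of the difference is 6 × √(2/41) = 1.325. Suppose there is no treatment effect and the ratings in one arm are shifted by b points. The noncentrality is b/1.325, and the two-sided t-test on 80 degrees of freedom rejects with these probabilities:

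| Assumed rating bias b (CAINS points) | b/1.325 | False-positive rate |
|---|---|---|
| 0 | 0 | 5.0% |
| 0.5 | 0.38 | 6.6% |
| 1 | 0.75 | 11.6% |
| 1.5 | 1.13 | 20.1% |
| 2 | 1.51 | 32.0% |

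For an assumed SD of 5 to 8, a 1-point bias gives 15% down to 9%, and a 2-point bias gives 43% down to 20%.

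Every b here is an assumption, since the documents give no figure for rating bias. The calculation also uses a two-sample t-test, whereas section 6.1 plans a repeated measures ANCOVA. It shows what biased ratings would do in any trial of this size. It does not show that this plan produces them.

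**The case for a change.** The strongest case for a change is that the protocol asserts blinding without describing how it is kept. Who rates, who treats, who holds the allocation and who interviews are matters of conduct, which belong in a protocol rather than an SAP. The only role description given, in section 5.5, ties research assistants to the intervention. A rating made unblind cannot be repaired later, and one sentence would remove the doubt.

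Part of this stands. The protocol does not say that the assessor is a different person from the trained assistants, who delivers MCT Minus or supportive counselling, who runs the online randomisation and holds its result, or who holds the exit interviews and when. A sentence on these points would be a courtesy to the reader.

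It does not show an error, though. Section 5.4 already sets the binding requirement: whoever rates must not know the arm. A team that meets it has to keep the rater away from treatment delivery, from the allocation and, until the last rating, from interviews about the therapy. That follows from the requirement whether or not each step is spelled out. Training in the content of MCT is not knowledge of allocation, and the idea that a trained rater would recognise the material in a patient's answers is conjecture.

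The suggested additions go further than correcting anything. Recording the assessor's guess of the arm and asking participants not to mention their therapy are good practice and usually sit in a manual. Coded arm labels for the analyst are commonly left to the SAP, which is not shown. Nor can a formal split of roles be called free of cost: the number of assistants is not given and recruitment covers three regions.

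**Conclusion.** No change to the plan follows. The protocol states that one blind research assistant makes all the assessments, and nothing else in it contradicts that. The overlap is one of job title, and the protocol leaves staffing detail unstated in a way that a competent team fills when it puts section 5.4 into practice. Carried out as written, the CAINS and PANSS ratings are blind and the comparison of arms on them is sound.

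This rests on taking the statement in section 5.4 at its word. If the assessor in fact delivered therapy or knew the allocation, the false-positive rate could rise from 5% to about 12% or 32% for assumed biases of 1 or 2 CAINS points at SD 6. That would be a departure from the protocol, not a result of following it.

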### **6. Data analysis and statistics**

#### **6.1. Quantitative data**

Repeated measures ANCOVA will be used to evaluate changes at pre, post and follow-up analysis due to the repeated-measure nature of the data whilst regression analysis will be used for identifying and measuring potential mechanisms of change for negative symptoms. Missing data on questionnaires will be replaced with case-mean substitution if fewer than 20% of the items were missing as this has been found to be a robust way of handling data missing on an item level (Fox-Wasylyshyn & El-Masri, 2005).

Preprocessing and analysis of fMRI data will be performed in the conn toolbox in Matlab, preprocessing of DWI and MRS data in FSL and LCModel, respectively, or equivalent software.

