##### **5.3. Outcome measures**

This study will use a combination of interviews and self-rated questionnaires to assess negative symptoms. The primary outcome measures will be the Clinical Assessment Interview for Negative Symptoms (CAINS) (Forbes et al., 2011), the Motivation and Pleasure Scale—Self-Report (MAP-SR) (Llerena et al., 2013), and the Positive and Negative Syndrome Scale (PANSS) (Kay et al., 1987) (with the PANSS negative factor proposed by Wallwork et al. (2012)). The CAINS was chosen as it has been developed to measure negative symptoms as defined by the NIMH consensus development conference (i.e., blunted affect, alogia, anhedonia, asociality and avolition) (Kumari et al., 2017). (We replaced the Brief

Negative Symptom Scale (BNSS) (Kirkpatrick et al., 2010) with CAINS as the BNSS has not been validated or translated into Swedish).

To identify and measure mechanisms of change, four measures will be used: the Dysfunctional Attitudes Scale (DAS) (Weissman & Beck, 1978) to measure the severity of defeatist attitudes; the Reflective Functioning Questionnaire (RFQ-8) (Fonagy et al., 2016) to assess metacognitive capacity; the Calgary Depression Scale for Schizophrenia (CDSS) (Addington et al., 1990) to measure depression; and the Internalized Stigma of Mental Illness Scale-9 (ISMI-9) (Hammer & Toland, 2017) to measure stigma. Finally, the World Health Organization (WHO) Disability Assessment Schedule (WHODAS) 2.0 (WHO, 2010) will be used as this has been suggested to be a more reliable measure than the Global Assessment of Functioning (GAF) (American Psychiatric Association (APA), 1987) for assessing a person's overall functioning (Gspandl et al., 2018).

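### Repeated measures ANCOVA over three visits, run conventionally, drops anyone who misses a visit; a likelihood-based mixed model would keep the post assessments already collected (optional improvement)

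*Protocol*

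**What the plan says.** Protocol section 6.1 names one method for change over time: "Repeated measures ANCOVA will be used to evaluate changes at pre, post and follow-up analysis due to the repeated-measure nature of the data". Section 5.4 confirms the three time points: "Pre-, post-, and follow-up assessments will be conducted by a research assistant who is blind to group allocation". The only missing-data rule is also in 6.1: "Missing data on questionnaires will be replaced with case-mean substitution if fewer than 20% of the items were missing". Its stated justification is "as this has been found to be a robust way of handling data missing on an item level".

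Section 5.1 expects losses. It says "41 participants in each arm will be needed" and then "We will aim to recruit 45 in each arm to allow for drop-out, group heterogeneity", with later analyses given as a further reason for the margin. It states no drop-out rate, SD or correlation between visits.

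Section 5.3 lists three primary measures (CAINS, MAP-SR and the PANSS negative factor), four mechanism measures (DAS, RFQ-8, CDSS and ISMI-9) and WHODAS 2.0. Section 1 lists change in all eight as an aim, so the 6.1 method is read here as covering all eight.

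**The concern.** Conventional repeated measures ANCOVA needs a complete row for each person. A participant assessed at pre and post but not at follow-up drops out of the whole analysis, including the post comparison to which they contributed data. Case-mean substitution fills a few missing items within a completed questionnaire; a missed visit leaves no items to average.

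Two things are at stake. One is precision, because collected assessments go unused. The other is bias: if people who did badly by post are more likely to leave before follow-up, those who remain are a selected group and the arm difference at post shifts. The direction depends on which arm loses its poor responders, so it cannot be predicted in advance.

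The point concerns the method the protocol names. It is not a complaint that a contrast, key visit or analysis set is left unnamed.

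**Working it through.** **Inputs.** From section 5.1: difference 4 CAINS points, power 0.85, significance level 0.05 (two-sided assumed), 41 needed and 45 recruited per arm. Assumed: drop-out rates, correlations and drop-out mechanism.

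**1. The plan's own figure.** The SD is not given, so it was back-solved. Normal approximation: SD = 4 × √(41/2) / (1.960 + 1.036) = 6.04. Noncentral t: SD = 5.97. The figure of 41 is thus consistent with an unstated SD of about 6, and nothing below depends on it being wrong.

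**2. Margin.** 1 − 41/45 = 8.9% total loss. Under complete-case analysis, losses at post and at follow-up share it: 1 − √(41/45) = 4.5% per visit.

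**3. Participants kept per arm**, with loss p at each later visit:

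| p | All visits, 45(1−p)² | Attended post, 45(1−p) | Post visits discarded, 45p(1−p) |
|---|---|---|---|
| 5% | 40.6 | 42.8 | 2.1 |
| 10% | 36.5 | 40.5 | 4.05 |
| 15% | 32.5 | 38.3 | 5.7 |

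**4. Power at post.** The baseline-adjusted SD is 5.97 × √(1 − r²), where r is the correlation between visits; this gives 5.70, 5.17 and 4.78 for r = 0.3, 0.5 and 0.6. The noncentrality is 4 / (adjusted SD × √(2/n)). Example: for r = 0.3 and n = 36.5 it is 4 / (5.70 × √(2/36.5)) = 3.00, giving power of about 84%.

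| r | Completers, p = 5 / 10 / 15% | All post attenders, p = 5 / 10 / 15% |
|---|---|---|
| 0.3 | 88 / 84 / 80% | 89 / 88 / 86% |
| 0.5 | 93 / 90 / 87% | 94 / 93 / 92% |
| 0.6 | 96 / 94 / 91% | 97 / 96 / 95% |

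The gain is about 1 to 6 points. Completers fall below the planned 85% in two of nine cells, both at r = 0.3.

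**5. Bias at post.** This was simulated with 8,000 trials per scenario, 45 per arm, SD 6, r = 0.6 between all visits and a true effect of 4 at post and follow-up. Everyone attends post. The chance of leaving before follow-up is 12% at no change, and its odds multiply by 2 or 3 per SD (6 points) of pre-to-post worsening. The Monte Carlo standard error is about 0.012.

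| Arm in which drop-out depends on worsening | Completers' post estimate, odds ratio 2 / 3 | Mixed model |
|---|---|---|
| Control only | 3.66 / 3.42 | about 4.0 |
| Intervention only | 4.23 / 4.33 | about 4.0 |
| Both | 3.90 / 3.74 | about 4.0 |
| Neither | 3.99 | about 4.0 |

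Varying r from 0.3 to 0.7 and loss from 5 to 15%, completers ranged from 2.93 to 4.67 and the mixed model from 3.94 to 4.05.

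**6. Follow-up.** Under the control-only mechanism, completers' follow-up estimate was 3.88 / 3.78 and the mixed model's 4.01 / 4.00. When drop-out was unrelated to scores, precision at follow-up barely differed (SD of the estimate about 1.09 against 1.08).

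**7. Limit.** If control-arm drop-out depends instead on the unseen pre-to-follow-up change, the follow-up estimate is 3.65 / 3.42 from completers and 3.70 / 3.50 from the mixed model. Most of the bias remains.

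**The case against.** The strongest reply is that the protocol never says complete cases. The method's name does not settle how a missed visit is treated, and a statistical analysis plan could specify a mixed-model implementation. That is fair, and the point is conditional on the conventional implementation. But the protocol does name the method, and section 5.5 has the main researcher doing the analysis, with statistical support only a possibility, so the default form is a realistic outcome.

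Second, the bias simulation suits the fix: everyone attends post and drop-out depends on observed scores, so the mixed model recovers 4.0 at post by construction. The power table uses a different pattern, with loss at post as well. Both observations stand. The simulation shows what complete-case analysis can cost under a plausible mechanism; it does not predict this trial.

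Third, the effects are modest. With the same mechanism in both arms, the shift of 0.1 to 0.26 points is at most about a quarter of a standard error of roughly 1.05. This stands and is why the point is optional.

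Fourth, the benefit is said to be confined to post. This holds for precision but not for bias, as step 6 shows.

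Two smaller points are also fair. The margin from 41 to 45 serves more than drop-out, so 8.9% is an upper limit on the allowance. And four scales are introduced as mechanism measures, although section 1 makes change in each of them an aim.

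**Conclusion.** The concern holds as an optional improvement. If the named method is run in its usual form, about 2 to 6 attended post visits per arm are discarded at 5 to 15% loss per visit, costing about 1 to 6 points of power at post. The better reason to change is bias: under the main drop-out mechanism, a true 4-point effect at post is estimated as 3.4 to 4.3 from completers and 4.0 from the mixed model. These sizes rest on a back-solved SD of about 6 and on assumed drop-out rates, correlations and mechanisms. If drop-out is unrelated to scores, completers are unbiased and only precision is lost.

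**What to change.** In section 6.1, replace the repeated measures ANCOVA clause with wording to this effect:

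> Each outcome measured at pre, post and follow-up (CAINS, MAP-SR, PANSS negative factor, DAS, RFQ-8, CDSS, ISMI-9, WHODAS 2.0) will be analysed with a likelihood-based linear mixed model of the post and follow-up values. Fixed effects will be arm, visit, arm-by-visit, the baseline value of that outcome and baseline-by-visit, with an unstructured covariance. All participants with any post-baseline assessment will be included in their assigned arm. The arm difference at each visit will be reported with its 95% confidence interval.

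Keep the regression analysis of mechanisms, the item-level substitution rule and the MRI paragraph as they are; MRI is done at pre and post only, so missing follow-up does not remove a post scan. Report the number per arm with no post-baseline assessment, since the model leaves them out.

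The cost is a change of wording and a different software routine, with no extra data, visits or participants. It should be settled before outcomes are analysed by arm. The model assumes data are missing at random, a weaker assumption than complete-case analysis generally needs but still an assumption. It does not repair drop-out before any post-baseline visit, or drop-out driven by unseen follow-up scores.

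### Protocol 6.1 lists the pre visit among the analysed visits and does not tie its repeated measures ANCOVA to the single 4-unit CAINS arm difference on which 5.1 sizes the trial

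*Protocol*

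**What the plan says.** Section 6.1 of the protocol gives the outcome analysis in one sentence: "Repeated measures ANCOVA will be used to evaluate changes at pre, post and follow-up analysis due to the repeated-measure nature of the data". Pre stands in the list on the same footing as post and follow-up. The sentence names no covariate, and it does not say whether the arm term or an arm-by-visit term carries the treatment comparison.

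Section 5.1 rests the sample size on a simpler comparison: "We have used t/z-test, with a power of 0,85, and a significance level of 0,05, to calculate sample size". The target is stated as "In order to find a difference of 4 units on CAINS", and the result is "41 participants in each arm will be needed". It mentions no repeated visits, no baseline adjustment and no visit to which the 4 units apply.

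Section 5.4 fixes the timing of the pre visit: "relevant demographic information and baseline measures will be completed before beginning the intervention".

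**The concern.** Pre is measured before any intervention, so under randomisation the expected arm difference there is zero. If pre is a level of the repeated factor and the arm term is averaged over all three visits, a visit that cannot show an effect is averaged in with two that can. A true difference at the protocol's own 4-point benchmark could then be reported below that benchmark or, without baseline adjustment, missed.

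If an arm-by-visit term is used, nothing is biased. But the baseline CAINS score then serves as a response, when it could reduce the variance of the arm comparison. In neither case does 6.1 lead to the one contrast on which 5.1 sized the trial.

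**Working it through.** **Inputs.** From 5.1: difference 4, power 0.85, significance level 0.05, 41 per arm. Assumed, because the protocol does not give them: a two-sided test, the SD, equal SDs and equal correlation ρ between visits, no missing data, and the pattern of effect over visits.

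**The plan's own figure.** No SD is stated, so 41 cannot be reproduced from the protocol alone. Solving backwards for 41 per arm gives SD 5.97 (two-sided t) or 6.04 (two-sided z). With SD 6.0 the two-sided z formula returns exactly 41. SD 5.97 is used below and gives power 0.850 for the sized two-group test.

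**1. Arm term over three visits, no baseline covariate.**
- Estimate: (0 + 4 + 4)/3 = 2.67.
- SD of a patient's three-visit mean: SD·√((1 + 2ρ)/3). At ρ = 0.5 this is 5.97 × √(2/3) = 4.875.
- Standard error: 4.875 × √(2/41) = 1.077. Ratio: 2.67/1.077 = 2.48. Power 0.69, falling to 0.61 at ρ = 0.7.
- If the effect is 4 at post and 2 at follow-up, the estimate is (0 + 4 + 2)/3 = 2.0, with power 0.45 to 0.39.

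**2. The same term, with pre also entered as a covariate.** The arm coefficient is two thirds of the baseline-adjusted coefficient for the mean of post and follow-up, and so is its standard error. A simulation (4000 runs, SD 6, ρ = 0.5, 41 per arm) gave 2.67 with standard error 0.631, against 4.01 with standard error 0.946 when only post and follow-up are responses; 0.631/0.946 = 0.667. The test statistic is therefore unchanged (power 0.99 in both), and only the estimate is diluted.

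**3. Arm-by-visit, pre kept as a level.**
- The 1-df pre-to-post contrast estimates 4. The SD of the change is SD·√(2(1 − ρ)). At ρ = 0.5 this is 5.97, standard error 1.319, ratio 3.03, power 0.85.
- For the 2-df test the squared deviations of (0, 4, 4) from their mean sum to 7.11 + 1.78 + 1.78 = 10.67. Noncentrality is (41/2) × 10.67/(5.97² × 0.5) = 12.27. On F(2, 160) the power is 0.88. For the pattern 4 then 2 it is 0.77 to 0.95 over ρ = 0.5 to 0.7.

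**4. Baseline-adjusted arm difference at one later visit.** Estimate 4. The SD is SD·√(1 − ρ²). At ρ = 0.5 this is 5.171, standard error 1.142, ratio 3.50, power 0.93.

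Power with 4 points at both later visits, 41 per arm:

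| ρ | Arm term, no covariate (estimates 2.67) | 1-df pre-to-post contrast (estimates 4) | 2-df arm-by-visit | Baseline-adjusted, one visit (estimates 4) |
|---|---|---|---|---|
| 0.3 | 0.78 | 0.72 | 0.75 | 0.88 |
| 0.5 | 0.69 | 0.85 | 0.88 | 0.93 |
| 0.7 | 0.61 | 0.97 | 0.985 | 0.987 |

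The advantage of column 5 over column 3 does not depend on the assumed SD: 2(1 − ρ) − (1 − ρ²) = (1 − ρ)², which is positive for every ρ below 1.

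**The case against.** A reader might infer that the planned analysis will report a true 4-point difference as about 2.7 and that the planned power is lost. The protocol does not support that, for three reasons.

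- 6.1 never names the arm main effect as the treatment test. Its stated purpose is to evaluate changes, which fits an arm-by-visit comparison at least as well, and 5.1 justifies the 4 units from a change score: "a change in total score of 4 points has been found to show a true change at a 95% confidence level". On that reading the 1-df contrast recovers 4, and the 2-df test has power 0.88 or more at correlations of 0.5 to 0.7 when the effect holds at both visits.
- ANCOVA implies some covariate. If it is the pre score of the same measure, the three-visit arm term loses no power.
- The value 2.67 needs equal effects at post and follow-up, which the protocol does not state.

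It is also fair to say that a protocol commonly leaves the tested term, the covariates and the primary visit to a statistical analysis plan. None is at hand here, so silence on those items is not in itself a fault. Keeping pre as a response level and testing arm-by-visit is a valid method.

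All of this stands, and it limits the point. What it leaves is that the protocol has already chosen a model and listed pre among its visits. That wording admits a diluted arm term, and its unbiased reading uses the baseline score less efficiently than it could.

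**Conclusion.** The point holds as an improvement to the analysis, not as a fault that must be fixed. Section 6.1 lists pre as an analysed visit and is not tied to the single difference sized in 5.1. The consequence depends on the reading: an estimate of 2.67 and power 0.69 to 0.61 for an unadjusted three-visit arm term; the same diluted estimate but no loss of power if pre is also a covariate; no bias under arm-by-visit.

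Against the unbiased readings, the gain from a baseline-adjusted contrast at one visit is moderate. Over correlations 0.3 to 0.7 its power is 0.88 to 0.99, against 0.72 to 0.97 for the 1-df change contrast and 0.75 to 0.985 for the 2-df test. At 0.7 it is practically level with the 2-df test.

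The powers rest on a back-solved SD and assumed correlations, complete data, and 4 points at both later visits. The ordering of the baseline-adjusted contrast over the change contrast does not rest on the SD.

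**What to change.** In 6.1, state that:

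- the responses are the post and follow-up scores;
- the pre score of the same measure is a covariate only, never a response;
- the model contains arm, visit and arm-by-visit;
- the CAINS result is the 1-df baseline-adjusted arm difference, with its 95% CI, at one visit that the sponsor names in advance.

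In 5.1, say that the 4-unit difference refers to that same visit. Which visit it is remains the sponsor's choice; the protocol does not favour either. The same form can serve the other scales.

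The cost is a few sentences, settled before outcome data are seen. It needs no extra patients, visits or measurements, since the baseline scores are already collected under 5.4.
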